This study will focus on two objectives. First, it will provide data about the effectiveness of the Welcome Basket (WB) intervention, which has demonstrated feasibility and is associated with positive outcomes⁹. In the proposed trial, we hypothesize that the WB will be proven effective as compared with treatment as usual (TAU) in service use and clinical domains. Baseline measures will be completed in the week prior to discharge, at 4 weeks post discharge to assess short-term impact, and at 6 months post-discharge to assess sustainment of gains. Assignment for this single blind trial will be random.

Figure 1 – Trial Diagram, Measure Summary, Study Timeframe

Measures:	Community Functioning (primary) Hospitalization Quality of Life Community Involvement Symptomatology Recovery Process Engagement
------------------	---

Along with the intended outputs of the Welcome Basket (WB) Trial were a clinical outcome paper and a process paper on WB implementation. During initial meetings for the process paper, we have discussed that it is necessary to interview the peer support workers on the trial in order to get an in depth understanding of how peer support is implemented. The process paper will illustrate how peer support workers implement peer support at an individual level as well as the successes and barriers that occur for peer workers at both the individual and system levels. This understanding will allow for recommendations to be made as to how peer support work can be done successfully and how to best troubleshoot challenges that may arise during

Study Timeframe

Activity	Months:	0	6	12	18	24	30	36
Staffing/Setup		>>						
Recruitment (6/month)		>>>>>>>>>>>>>>>>>>>>>>>>>>>>						
Intervention			>>>>>>>>>>>>>>>>>>>>>>>>>>>					
	>>							
Measures		>>>>>>>>>>>>>>>>>>>>>>>>>>>>>>>						
Data Analysis			>>>				>>>	
Knowledge Exchange							>>>>>	

2. What are the planned trial interventions

Experimental Interventions

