2. Welcome Basket (Brief) Intervention: The brief version of the Welcome Basket (WBbr) was developed based upon the observation in feasibility testing that for some participants much of the benefit of this approach appeared to be centred upon the visits immediately prior and subsequent to discharge. In the WBbr the same core components will be present, albeit in an abbreviated form with one 30-60 minute visit in the week prior to discharge and a single, 3-hour visit in the week subsequent to discharge in which the welcome basket would be delivered, core CAT strategies discussed and implemented, and some basic orientation to community resources undertaken. This brief version of the intervention has not to date been studied.

Treatment As Usual

Treatment as usual (TAU) involves the typical discharge procedures for clients from Unit 2, Forensic and EPU wards at CAMH. It includes referral to outpatient psychiatric services and relevant community supports with the transition facilitated by inpatient social work staff.

Controlling for Case Management

It will be a requirement that all clients enrolled in the study are engaged in some form of community-based case management along with medical follow-up. This strategy will assist in controlling for outcome variance impacted by conditions other than the intervention being studied.

Peer Support Worker Training and Clinical Context

Inpatient and outpatient clinicians and administrators are familiar with the intervention and regarded it positively from feasibility testing through to its current, ongoing delivery. There are currently 5 Peer Support Workers on staff who are extensively trained in the WB intervention. They were initially trained by [name] who developed the original WB intervention in New Haven and were trained in compensatory intervention by CAT specialists in collaboration with Drs. [name] and [name].

Participant Allocation and Blinding

For the trial, blocked randomization at a 2:2:1 ratio (TAU:WB:WBbr) will be employed to ensure balance in sample size between treatment and control groups. Stratification will not be employed as feasibility study findings did not suggest significant variance attributable to demographic or treatment history factors. Study measures will be collected by research assistants blinded to the treatment condition.

3. What are the planned inclusion/exclusion criteria?

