1. Participants will be adults, 18 years of age or older, with a chart diagnosis of a schizophrenia spectrum mental illness or bipolar disorder with psychotic features confirmed by Module B (psychotic symptoms) of the Structured Clinical Interview for DSM-5 (SCID-

5)¹⁵. All participants will be on CAMH inpatient units at the time of recruitment and will have been in inpatient care for close to or more than 2 weeks. This timeframe is guided by the rationale and experience indicating that an overly brief period of hospitalization circumscribes the relevance of the intervention.

2. Participants will be returning to places of residence in the Greater Toronto Area (catchment of CAMH).
3. Participants must have been referred to outpatient case management.
4. Proposed housing arrangements must be stable and conducive to the intervention. If homelessness or emergency shelter residence appears likely, or boarding home policy precludes any external staff from entering the premises, such individuals will be excluded.
5. Proficiency in English.

4. What are the proposed primary and secondary outcome measures and qualitative feedback?

Primary Measure: Community Functioning will be assessed with the Multnomah Community Ability Scale (MCAS)¹⁶, a 17-item scale assessing domains of functionality including health, adjustment to living, social competence, and behavioral problems (completed at all time points). This measure best reflects the primary aim of this intervention: to support a greater degree of illness self-management, independence, and level of community activity. The MCAS will be scored based upon interviews with participants primary clinician (inpatient for baseline and case managers for post and follow up measures).

Secondary Measures (All inventories have established psychometrics with this population.)

1. Hospitalization as assessed at 4 weeks and 6 months post-discharge (number of rehospitalizations and lengths of stay captured through case manager report and verified through hospital electronic database if a CAMH hospitalization).

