2. Quality of Life (QoL) will be assessed with the Satisfaction With Life scale (SWLS)¹⁷, an 18-item scale that has subscales assessing living situation, social relationships, work, self and present life. SWLS will be assessed post intervention and at follow up (would not be valid during inpatient stay due to contextual confounds with items). QoL will also be assessed using the Social Support Survey¹⁸, a 19 item scale that measures emotional/information support, tangible support, affectionate support and positive social interaction (all time points)
3. Symptomatology will be measured using the 53 item Brief Symptom Inventory¹⁹ (all time points) and the 23 item GAIN Short Screener (GAIN-SS)²⁰ (all time points).
4. Recovery Process Engagement will be measured with the brief, 10-item version of the Personal Recovery Outcome Measure²¹ (all time points).
5. Community Involvement will be assessed with the 11 item Community Integration Scale which was developed for the At Home study with a comparable population to assesses psychological and behavioural community engagement²². Community Involvement will also be assessed with the Social Functioning Scale²³. Community Involvement will be assessed post intervention and at follow up (would not be valid

during inpatient stay due to contextual confounds with items).

6. Descriptive Measures include core demographics (gender, ethnicity, sexual orientation, age, education, etc.; assessed at time 1) and service use history (history of hospitalization, physical and mental health service use, community services; assessed at baseline and updated at each contact). Amount of contact in hours/month with a person or persons (other than providers; e.g., family) regarded as an important supports by participants will be captured. This will help in determining if non-service supports are a relevant covariate in considering outcomes.

Qualitative interviews: The current peer support workers involved with the Welcome Basket study will be asked to participate in an open-ended interview that will ask how they engage in peer support work with clients as well as successes and challenges that occur at both the individual and system level. After obtaining consent, the graduate research assistant will conduct a 1-hour interview with the peer worker (see Appendix 2).

5. What is the proposed sample size and analysis strategy?

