The primary objective of this trial is to test a difference between the full WB intervention and the control condition with an alpha level of 0.05 and a power of 80%. An additional pilot study of the WB brief intervention is proposed with an approximate 0.05 alpha level, at 50% power. While multiple testing has not been corrected for, the intention is not to power this trial to detect these differences but rather to gather the necessary preliminary data on the average effect and variance of response in the brief intervention group to determine whether further testing is indicated and sufficient data to allow for power calculations for a follow-up trial. The target sample is thus 125 participants with a 2:2:1 randomization ratio of TAU to full WB to WB brief. Accounting for an estimated 13% attrition rate (observed in the feasibility study) this sample size would result in 44 completers/group for the main intervention and control groups and 22 completers in the brief intervention group. Based on MCAS means and the pooled standard deviation observed in the feasibility study (assuming no beneficial change in MCAS in the control group), and using a superiority trial power calculation²⁴, this sample size will allow for the detection of medium effect sizes at 80% power.

The data analysis strategy is as follows: (1) We will examine treatment and control groups at baseline on demographic variables and flag any clinically significant differences that might confound outcomes. (2) We will develop a descriptive profile of session attendance. We will consider the participant as having been exposed to the intervention if they have attended at least 50% of sessions. (3) We will compare the full WB intervention group and the control group on changes in hospitalization, community involvement, community functioning, quality of life, and symptomatology from baseline to week 4 post discharge. Analysis of variance (ANCOVA) will be used for this comparison with the above variables being the dependent measures and treatment group being the independent variable controlling for MCAS scores at baseline. (4) Differences over time in these variables from baseline, to 4 week and 6 month follow up measures will be

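### Minor, secondary outcomes only: the week-4 ANCOVA does not use the collected baselines of the BSI, GAIN-SS and Social Support Survey as covariates, which gives up precision at no saving

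*Combined protocol and SAP*

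**What the plan says.** Section 5, analysis step (3), compares full WB with control on "changes in hospitalization, community involvement, community functioning, quality of life, and symptomatology from baseline to week 4 post discharge". The method is ANCOVA, with "treatment group being the independent variable controlling for MCAS scores at baseline". One covariate therefore serves every outcome listed.

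Section 4 shows which of these outcomes have a baseline of their own:

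- **Collected at all time points:** MCAS (primary), the BSI and GAIN-SS (item 3: "Symptomatology will be measured using the 53 item Brief Symptom Inventory", with the GAIN-SS alongside), and the Social Support Survey (item 2, under quality of life).
- **No baseline by design:** SWLS (item 2) and both Community Involvement scales (item 5), because their items would not be valid during the inpatient stay.
- **No baseline score on the same measure:** rehospitalization (item 1: "Hospitalization as assessed at 4 weeks and 6 months post-discharge").
- **Collected at all time points but not listed in step (3):** the Personal Recovery Outcome Measure (item 4).

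Step (4) is a separate mixed model over baseline, 4 weeks and 6 months. The sample size rests on MCAS alone: "Based on MCAS means and the pooled standard deviation observed in the feasibility study".

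**The concern.** A scale's own baseline is usually the strongest available predictor of its later score. Baseline MCAS, a functioning score taken from an interview with the clinician, is an indirect substitute for it when the outcome is a symptom or social-support scale.

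Step (3) leaves the dependent variable slightly open. If it is the change from baseline, which is the natural reading, the own baseline is used with its slope fixed at 1. If it is the week-4 score, step (3) does not use the own baseline at all. Either way the treatment contrast is unbiased under randomisation, but its standard error is generally larger than it need be.

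What is at stake is the precision of three secondary instruments in one of two planned analyses. With 44 completers per main arm and a size chosen for MCAS, these scales have little precision to spare.

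**Working it through.** **The plan's own figure.** 125 participants at 2:2:1 gives 125 × 2/5 = 50 per main arm. With 13% attrition, 50 × 0.87 = 43.5, which the plan rounds to 44. I use n = 44 per arm.

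**Assumed inputs.** The documents give no correlations or SDs for the three scales. Let r be the correlation between baseline and week 4, and k the baseline SD divided by the week-4 SD, with the week-4 SD set to 1. I take r = 0.5-0.7 and k = 0.8-1.25. Equal SDs cannot be presumed, because the first assessment is made in hospital and the next in the community: "Baseline measures will be completed in the week prior to discharge, at 4 weeks post discharge to assess short-term impact".

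**Change-score reading, MCAS unrelated to the change.**

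- Residual variance of the change score: 1 + k² − 2rk
- Residual variance with own baseline as covariate: 1 − r²
- Effective n = 44(1 − r²)/(1 + k² − 2rk)
- Loss = 44 − effective n = 44(k − r)²/(1 + k² − 2rk), which is zero when k = r

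Example, r = 0.5 and k = 1: 44 × 0.75/1.00 = 33.0, a loss of 11.0, with the SE larger by a factor of √(1/0.75) = 1.155.

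| k | r | Effective n | Loss per arm | SE ratio |
|---|---|---|---|---|
| 0.8 | 0.5 | 39.3 | 4.7 | 1.058 |
| 0.8 | 0.6 | 41.4 | 2.6 | 1.031 |
| 0.8 | 0.7 | 43.2 | 0.8 | 1.010 |
| 1.0 | 0.5 | 33.0 | 11.0 | 1.155 |
| 1.0 | 0.6 | 35.2 | 8.8 | 1.118 |
| 1.0 | 0.7 | 37.4 | 6.6 | 1.085 |
| 1.25 | 0.5 | 25.1 | 18.9 | 1.323 |
| 1.25 | 0.6 | 26.5 | 17.5 | 1.288 |
| 1.25 | 0.7 | 27.6 | 16.4 | 1.262 |

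**MCAS related to the scale.** Suppose MCAS correlates 0.5 with the scale's baseline and relates to week 4 only through it. With MCAS in both models, the change-score residual variance is 0.75(k − r)² + 1 − r². At r = 0.5, 0.6, 0.7 the losses are 3.6, 2.0, 0.6 (k = 0.8); 8.8, 6.9, 5.1 (k = 1); and 15.8, 14.6, 13.5 (k = 1.25).

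**Simulation.** With 44 per arm and MCAS in all models, the losses at r = 0.5 and 0.7 were 4.0 and 0.2 (k = 0.8), 10.2 and 6.5 (k = 1), and 18.8 and 15.7 (k = 1.25). Mean estimates under no effect lay within 0.004 SD of zero, so neither analysis is biased.

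**Outside the chosen inputs.** At r = 0.3 and k = 1.25, 44 × 0.91/1.8125 = 22.1, a loss of 21.9.

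**Week-4-score reading.** Let q be the MCAS-to-outcome correlation, and let MCAS add nothing once the own baseline is in the model. Effective n is 44(1 − r²)/(1 − q²). At q = 0.2 the loss is 9.6, 14.7 and 20.6 for r = 0.5, 0.6 and 0.7, whatever k is.

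**Cost of the extra covariate.** About 44/84 ≈ 0.5 completer per arm, where 84 = 88 − 3 − 1 is approximately the residual degrees of freedom.

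**The case against.** The strongest reply is that this is a preference for efficiency and not an error. On the natural reading each own baseline is already used through the change score, the estimate is unbiased, and no power is claimed for these scales. That is right, and it is why the point is minor. What stands is that a fixed slope of 1 is generally not the best slope, and the data to estimate it will be in hand.

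Second, the size is assumed. It is, and the low end can vanish: the loss is zero at k = r, and the simulation gives 0.2 in one cell. Where the true loss is that small, the half-completer cost of the extra covariate cancels it.

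Third, other parts of the plan might fill the gap. Section 4, item 6, contemplates contact with non-service supports as a possible covariate, and step (1) flags baseline demographic differences. Neither supplies a scale's own baseline. Step (4) does model baseline as a response, but the text does not say that the arms share a common baseline mean. With complete data, categorical time and free baseline means, its week-4 group-by-time contrast is essentially the change-score contrast, so it does not recover the loss.

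A reader might infer that the plan ignores baseline symptoms altogether, or that the comparison is biased. The change wording in step (3) and the randomisation do not support either.

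**Conclusion.** The point holds as a minor improvement for three secondary scales: the BSI, GAIN-SS and Social Support Survey. I am confident that their own baselines are missing from the named covariates, and not confident in any single figure for the cost.

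On the change-score reading, the loss is from about 0 to about 19 of 44 completers per arm for r = 0.5-0.7 and baseline/week-4 SD ratios of 0.8-1.25, and 7-11 at equal SDs. Other plausible inputs fall outside this range, so it is an illustration and not a bound.

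Three stronger inferences are not supported:

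- **That the trial is underpowered as a result.** The stated power is for MCAS, which is already adjusted for its own baseline. The type I error rate is also unaffected.
- **That all secondary outcomes are affected.** SWLS, the Community Integration Scale, the Social Functioning Scale and hospitalization have no own baseline score to adjust for.
- **That some gain is guaranteed.** It depends on how far the SD ratio lies from r, which the documents do not tell us.

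**What to change.** Keep step (3)'s outcome list and its restriction to full WB versus TAU. After the phrase that names baseline MCAS as the covariate, add: *and, for the BSI, GAIN-SS and Social Support Survey, the baseline score of the same measure*.

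The MCAS sentence needs no rewriting. Once a measure's own baseline is in the linear model, analysing the change or the week-4 score gives the same treatment estimate, so the clause works on either reading.

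Two short clarifications should go with it:

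- SWLS, the Community Integration Scale, the Social Functioning Scale and hospitalization, which have no own baseline score, are compared at week 4 adjusting for baseline MCAS.
- If the Personal Recovery Outcome Measure is also analysed at week 4, it is adjusted for its own baseline in the same way.

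Step (4) need not change. Constraining baseline means to be equal across arms there is an optional equivalent. The wording should be settled before any unblinded analysis, so that the covariate cannot appear to have been chosen from the results.

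The cost is one degree of freedom in each affected secondary model, with no new data, visits or participants.

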analyzed using mixed-effects linear modeling. For these analyses, a time effect will reflect changes across groups over time, and the group-by-time interaction will reflect changes over time between the groups. For all analyses $p < .05$ will be used as the level of significance with Cohen's d effect sizes reported. A blinded interim analysis will be conducted to determine if the sampling estimation needs to be revised. Plotting, mean and variance estimates will be calculated using the data from the WB brief treatment arm and compared with the control and full treatment.

All interviews will be recorded and transcribed by the graduate research assistant and undergraduate volunteers. Two independent researchers will code the transcripts using thematic content analysis²⁵, in order to analyze common themes that occur within the data. The PI will resolve any discrepancies that occur within the qualitative analysis. The themes will be brought back and discussed with the peer workers and WB team. Any other comments or themes that arise from this discussion will be documented using field notes²⁶.

6. Data Management and Integrity

The basic protection against risk in this study will be provided by [name] (study PI). The PI will have primary responsibility for monitoring of participants during the entire time they participate in the study. The PI will meet regularly with study personnel to review accrued data, data confidentiality, and adherence to protocol design, recruitment, and participant complaints. During meetings the Study PI will also review the enrollment data, the accrual and integrity of clinical data, and any adverse event associated with the various components of the study. If a serious adverse event occurs during the study, it will be reported to REB.

All data pertaining to a participant's involvement in this study will be coded and stored in locked offices. This information will only be accessible to the research team. In unusual cases, a participant's research records may be released in response to a court order. If the research team learns that a participant or someone with whom the participant is involved with is in serious danger or harm, an investigator will inform the appropriate agencies as per legal or regulatory requirements.

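### Step (4) states no baseline adjustment, so its 6-month WB-TAU contrast is probably a difference in change from baseline: valid, but less precise than the data allow

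*Combined protocol and SAP*

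**What the plan says.** Protocol section 5 sets out two between-arm analyses. Step (3) compares full WB with TAU at week 4 by ANCOVA and states its adjustment, which is baseline MCAS. Step (4) covers the longer period: "Differences over time in these variables from baseline, to 4 week and 6 month follow up measures will be" analysed by mixed-effects linear modelling. It names a time effect and says that "the group-by-time interaction will reflect changes over time between the groups". It gives no baseline covariate, equal-baseline constraint, group main effect, coding of time, covariance structure or named 6-month contrast.

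Section 1 gives the 6-month visit the purpose of showing whether gains last. Step (4) is the only between-arm analysis that reaches it.

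Section 4 says who informs the MCAS ratings: "inpatient for baseline and case managers for post and follow up measures". It also says that the Satisfaction With Life scale (SWLS) and the community involvement scales are not collected at baseline.

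On size, section 5 says the "target sample is thus 125 participants with a 2:2:1 randomization ratio of TAU to full WB to WB brief", leaving "44 completers/group for the main intervention and control groups and 22 completers in the brief intervention group", and that "this sample size will allow for the detection of medium effect sizes at 80% power".

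**The concern.** Step (4) lists baseline among the modelled time points and takes the treatment effect from the interaction. In the usual fit of such a model each arm has its own baseline mean. The 6-month interaction contrast then subtracts the chance baseline difference between arms in full, although randomisation makes the expected difference zero. A baseline-adjusted analysis subtracts only the part that predicts the follow-up value.

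What is at stake is the precision of the sustainment result for MCAS and the other outcomes measured at all time points. The trial has little to spare: 44 per arm gives 80% power only at about d = 0.60. A second consequence is that a week-4 estimate read from step (4) could differ from the step (3) ANCOVA merely because one adjusts for baseline and the other does not.

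**Working it through.** **Inputs from section 5.** 125 participants at 2:2:1, so 50 TAU, 50 WB and 25 brief WB; attrition 13%; alpha 0.05; power 80%. Sidedness is not stated, and I take two-sided.

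**Assumptions, not in the documents.** The correlation rho between baseline and 6 months; equal SDs at the two visits; time coded as a factor; complete data. The last three, except the coding of time, are varied below.

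**The plan's own figure.** 50 × 0.87 = 43.5 (stated 44) and 25 × 0.87 = 21.75 (stated 22), so the completer counts reproduce. With 44 per arm the detectable difference at 80% power, in units of a single-visit SD, is 2.8016 × √(2/44) = 0.60 (one-sided, 0.53). The plan's claim of a medium effect carries no number, and the MCAS means and SD are not given, so the 80% cannot be checked further.

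**Variance of the 6-month WB-TAU contrast, n per arm, SD = 1.**

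- Change from baseline: 2 × 2(1 - rho)/n
- Baseline-adjusted or constrained: 2 × (1 - rho²)/n
- Ratio, adjusted over change: (1 + rho)/2, so the information lost is (1 - rho)/2

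Example at rho = 0.5, n = 44: 2 × 1.00/44 = 0.0455 against 2 × 0.75/44 = 0.0341, a ratio of 0.75. A generalised least squares calculation for the three-visit model, with free and with common baseline means, gave the same two variances.

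| Assumed rho | Information lost | Detectable d at 80% power, change v adjusted | Power at d = 0.5 | Power at d = 0.64 |
|---|---|---|---|---|
| 0.3 | 35% | 0.71 v 0.57 | 51% v 69% | 72% v 88% |
| 0.5 | 25% | 0.60 v 0.52 | 65% v 77% | 85% v 93% |
| 0.7 | 15% | 0.46 v 0.43 | 86% v 91% | 97% v 99% |
| 0.9 | 5% | 0.27 v 0.26 | above 99% for both | above 99% for both |

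Powers use the normal approximation. The 0.64 is the feasibility effect for community functioning in section 2. It comes from participants who received WB, so it serves only as an illustration of a between-arm effect.

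Below rho = 0.5 the change contrast is also less precise than ignoring baseline, because 2(1 - rho) then exceeds 1. At rho = 0.3 the variances are 1.4 and 1.

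**With dropout.** Starting from 50 per arm, with half of the 13% lost after baseline, half after week 4, and all available data used, the loss is 32%, 23% and 13% at rho 0.3, 0.5 and 0.7.

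**With unequal SDs.** If k is the baseline SD divided by the 6-month SD, the loss is 1 - (1 - rho²)/(1 + k² - 2·rho·k). At rho 0.3, 0.5 and 0.7 this is 25%, 14% and 4% for k = 0.85, and 47%, 40% and 33% for k = 1.2.

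**The case against.** The strongest reply is that step (4) is silent rather than wrong. A model with time as a factor and group-by-time terms only at the two follow-up visits is already the constrained model, and the text names no group main effect. It is true that the free baseline mean is an inference. But time plus group-by-time, fitted in the ordinary way, still gives each arm its own baseline mean. The constrained form needs a deliberate step that the plan does not state, whereas step (3) does state its adjustment.

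Second, a reader might infer that 15% to 35% of the information is certainly wasted. The documents do not support that: the range is only (1 - rho)/2 at a chosen rho of 0.7 to 0.3 with equal SDs. The change of MCAS informant and setting after baseline could plausibly lower rho, but no figure is given. At rho 0.7 or above the loss of power is small.

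Third, a reader might infer bias, or a fault in the week-4 comparison. Neither follows. Both models are valid under randomisation, and step (3) already adjusts MCAS for its baseline.

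Fourth, an equal-baseline constraint presumes that baseline comes before allocation and any intervention contact. Section 1 puts baseline in the week before discharge, and section 2 puts the WB meetings in the two weeks before discharge, so some WB baselines may follow a peer meeting. This objection stands as a limit on the fix. It does not favour the unadjusted model: with equal SDs, a baseline shift of size δ moves the change contrast by the whole of δ and the adjusted contrast by only about rho × δ. Nor does it justify restricting the analysis to participants whose baseline came first, since that would drop randomised participants.

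**Conclusion.** The point holds as a matter of precision and specification in the 6-month sustainment analysis. As written, step (4) would most naturally give a difference in change from baseline where a more precise baseline-adjusted contrast is available from the same data. Over the assumed rho of 0.3 to 0.9 the size runs from material to slight, and the documents do not show where in that range the trial lies. The equivalence with a change score is exact only with complete data and time as a factor. Under dropout it is close, and a linear time term or a joint two-degree-of-freedom interaction test would be a different quantity. The point does not apply to SWLS or the community involvement scales, which have no baseline. The change is worth making because it costs little and baseline adjustment is not less efficient in large samples, whatever rho is.

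**What to change.** In step (4), for the outcomes measured at all time points (MCAS, Social Support Survey, Brief Symptom Inventory, GAIN-SS, and the Personal Recovery Outcome Measure if it is analysed):

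- Treat time as a three-level factor and name the covariance structure.
- Either constrain the baseline mean to be equal across arms, with group-by-time terms only at week 4 and month 6, or model week 4 and month 6 with that outcome's own baseline as a covariate-by-time term. Choose one in advance.
- Report the WB-TAU difference at 6 months, with its confidence interval, from that model.

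For SWLS and the community involvement scales, compare the arms directly at week 4 and month 6.

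Keep all randomised participants. State that baseline is to be completed before allocation and before the first peer meeting. Where it was not, use the covariate form rather than the equal-mean constraint and report a sensitivity analysis.

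The cost is a few lines in the analysis section, one more modelling choice to pre-specify and one sensitivity run. No new data or participants are needed.
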